3. The study information will be explained to them at their individual bedside cubicles or a quiet corner of the nursing unit for semi-ambulant participants. Time will be given for consideration to the study. All questions asked will be answered. Upon verbal agreement, the consent will be taken using the appropriate ICFs attached.
4. The nurse-in-charge/doctor-in-charge of the patient will be notified of the participant's agreement to the study.

Study day process

5. Arrangement will be made with the nurse-in-charge to synchronize the daily skin assessments with the study assessment to avoid unnecessary exposure.
6. An initial baseline assessment (Day 0) will be conduct on the participant's buttocks, posterior aspect of thigh and perineal region. The subject will be placed on a lateral comfortable position.
7. Observations made will include the amount and extent of denudement, exudate level, redness, signs of infection and the skin condition.
8. A baseline photo will be taken prior treatment.
9. Concealed treatment codes placed in a sealed opaque envelope will be used for randomizing the cluster. Each nursing units will be asked to draw the sealed envelope. With the sealed envelopes contained numbers 1 to 3 where 1 = Standard of care (control), 2 = Treatment regimen 1, 3 = Treatment regime 2. Each draw will determine the allotted treatment for the study site to adopt.
10. The treatment products will be issued to the nurse for application.
11. The treatment regimens will be applied as per manufacturer's recommendation.
12. Patients will be followed up three times a week for a maximum of 21 days, or until the IAD has healed or discharged from the study site.
13. Each review (including baseline assessment), photos will be taken to document the extent of the IAD over the buttocks and/or thighs and/ or perineal region.
14. All assessments will be made using IADS-D and GLOBIAD tool. Permissions to use the assessment tool has been given.
15. On Day 3, 5 and 7, an assessment will be made to the skin appearance if the IAD has not resolved.
16. Patients on treatment regimens will be identified using visual cue - different flower icons. Patients on control regimens will be treated as per hospital policy on data management
17. All collected data will be entered into the CRF.
18. Upon completion of the data collection, the data will be transcribed into EXCEL and validated independently by two different assigned persons.

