19. The validated data in EXCEL will be imported into SPSS and R for data analysis on a later date.

Data collection

Baseline parameters and other outcome measures that will be collected include the pain scores, classification of IAD and healing rates, episodes of incontinence, deterioration to PI or development of other adverse events (Kon et al., 2017) will be collected based on the case record form. Subsequently, 4 more assessments will be made on the participants on the progress of the IAD following treatment(s)/control regimens.

Data Analysis plan

All data will be entered into a Microsoft Office Excel 2013 and independently verified for accuracy of the transcription. The data will then be imported into Statistical Package for the Social Sciences (SPSS) IBM Version 24 and R for analysis and coding. Descriptive analysis including means and standard deviations or medians and interquartile ranges for the numerical variables and frequencies for categorical variables will be used to describe the study sample characteristics. ANOVA will be used to analyse for group differences. The measure of effect (risk difference or mean difference) and a confidence interval or measure of variation will be examined. The intra-cluster correlation coefficient (ICC) will be examined with an ICC of 0.10 used as the acceptable determine for cluster independence during observations (Thomson 2012). Multivariate regression will be used to evaluate the effect of treatment regimens, adjusting for risk factors. A significance level of 0.05 will be used.

We will measure skin characteristics by an independent wound nurse clinician to determine if the photographs reflected any change in skin, size of redness, skin infection or other changes during the follow-up of days 1, 3, 5 and 7 after application of the product. Photographs will be examined to detect any signs of improvement or deterioration in skin condition – redness, maceration of skin and skin erosion (Van de Bussche et al., 2018). A copy of the photograph assessment form is attached. The outcome measures include the pain scores, assessment scores for IAD and healing rates, episodes of incontinence, deterioration to PI or development of other adverse events (Kon et al., 2017).

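### The plan names one group test for outcomes of several kinds and gives no method for unequal time under observation, so untimed comparisons of incontinence and harms would favour an arm observed for less time

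*Combined protocol and SAP*

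**What the plan says.** Under Data Analysis plan in the combined protocol and SAP, the between-group analysis rests on four sentences:

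- The test: "ANOVA will be used to analyse for group differences".
- The effect measure: "The measure of effect (risk difference or mean difference) and a confidence interval or measure of variation will be examined".
- A second treatment-effect analysis: "Multivariate regression will be used to evaluate the effect of treatment regimens, adjusting for risk factors". Family, link, outcome and offset are not given.
- The level: "A significance level of 0.05 will be used".

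Besides pain scores, the Data collection section lists "classification of IAD and healing rates, episodes of incontinence, deterioration to PI or development of other adverse events". The Data Analysis plan repeats most of this list and adds IAD assessment scores. Step 14 of the Study day process names IADS-D and GLOBIAD as the assessment tools.

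On time observed, step 12 says: "Patients will be followed up three times a week for a maximum of 21 days, or until the IAD has healed or discharged". Step 15 adds skin assessments on three named days in the first week, only for IAD that is still present. Data collection gives four post-baseline assessments, and the Data Analysis plan describes photographs over a day 1/3/5/7 schedule. No section gives a person-time denominator, an offset, a time-to-event method, a common window for all patients or a rule for discharge.

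**The concern.** There are two separate gaps.

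The first is the match of method to outcome. ANOVA compares means and can serve for pain and IADS-D scores. A mean of category codes has no clear meaning. Healing and PI are yes/no or time-to-event outcomes, and incontinence episodes and adverse events are counts or events. The risk difference suits yes/no outcomes, but no model is attached to it. The regression could be of the right kind, but the text does not say.

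The second is time at risk. Observation stops when the IAD heals, which is what the regimens are meant to bring about, or when the patient goes home. A patient who heals or leaves early has fewer days in which an episode, a PI or an adverse event can be recorded. An arm with quicker healing or earlier discharge could then look better on incontinence and safer on harms with an unchanged daily rate. For healing the direction reverses: early discharge leaves less time in which healing can be seen, and so counts against that arm.

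**Working it through.** **No figure to reproduce.** The document gives no sample size, event rate, standard deviation or expected follow-up. Every input below is an assumption, except the 21-day cap (step 12) and the 7-day cap (the day 1/3/5/7 schedule).

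**Model.** Observation ends at a constant hazard h = 1/m per day and is cut at day c. Daily rates are identical in all arms, so any difference is an artefact of time observed.

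- Mean days observed = (1 − exp(−h·c))/h
- Expected episodes at an assumed 3 a day = 3 × mean days
- Crude risk of an event with daily hazard l = l/(l+h) × (1 − exp(−(l+h)·c))

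**Episodes, m = 7 v 10**

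- Cap at day 21: 7 × (1 − exp(−3)) = 6.65 days v 10 × (1 − exp(−2.1)) = 8.78 days. Episodes 20.0 v 26.3. Ratio 6.65/8.78 = 0.76, so about 24% fewer.
- Cap at day 7: 7 × (1 − exp(−1)) = 4.42 days v 10 × (1 − exp(−0.7)) = 5.03 days. Ratio 0.88, so about 12% fewer.

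**Wider gap, m = 7 v 14, cap at day 21:** 20.0 v 32.6 episodes.

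**Crude event risk, cap at day 21, m = 7 v 10**

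| Assumed daily hazard | m = 7 | m = 10 |
|---|---|---|
| 0.5% | 3.2% | 4.2% |
| 1% | 6.3% | 8.2% |
| 2% | 11.9% | 15.3% |

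For the first row: 0.005/0.14786 × (1 − exp(−3.105)) = 3.2%, and 0.005/0.105 × (1 − exp(−2.205)) = 4.2%.

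**Effect on the test.** A simulation used 1,500 runs, three arms, identical rates, no clustering, the 21-day cap and a one-day minimum stay. It gave these rejection rates at a nominal 5%:

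| Analysis | m by arm | n = 20 per arm | n = 50 | n = 100 |
|---|---|---|---|---|
| ANOVA, raw episode totals | 10, 10, 10 | 5% | 4% | 4% |
| ANOVA, raw episode totals | 10, 7, 7 | 17% | 39% | 64% |
| ANOVA, raw episode totals | 14, 7, 7 | 50% | 89% | >99% |
| ANOVA, episodes per day | 10, 7, 7 | 4% | 5% | 4% |
| Poisson with log(days) offset | 10, 7, 7 | 5% | 5% | 5% |
| ANOVA, 0/1 event at 1% a day | 10, 7, 7 | 4% | 6% | 7% |
| ANOVA, 0/1 event at 1% a day | 14, 7, 7 | 4% | 10% | 16% |

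The equal-follow-up row and the per-day row locate the cause. ANOVA keeps its size when time is equal or divided out. It loses its size when time is unequal and ignored.

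**The case against.** **ANOVA is not the only planned comparison.** This is correct. The plan also names a risk difference and an adjusted regression. Neither fills the gap as written: a crude risk difference ignores time at risk, and the regression has no stated outcome, family or offset.

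**The bias does not come from ANOVA.** This is also correct. A reader might infer that replacing ANOVA would remove it, or that ANOVA creates it. The table above shows otherwise, and a chi-square test on ever/never events would share the fault.

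**Nothing shows that the bias will occur.** It needs outcomes analysed as totals or ever/never, and follow-up that differs between arms. The document states neither. Incontinence episodes appear in a list that also covers baseline parameters, so a per-day or per-assessment figure is at least as plausible. That would remove most of the problem for this outcome. The case record form, which would settle it, is not in the document.

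**A lower PI risk may be real.** If a regimen heals IAD sooner and leaves fewer days in which it can deteriorate, a lower cumulative risk is arguably a benefit. This stands: cumulative risk and daily rate answer different questions, and the plan should say which it wants. Early discharge is the clearer source of bias.

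**Averaging of category codes is not stated.** This is true. The plan provides frequencies for categorical variables, but only to describe the sample. That the IAD classification comes from GLOBIAD is a reading of the text, not a statement in it.

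**Conclusion.** The point holds in conditional form. The analysis section does not match methods to its outcomes and, as a separate matter, has no provision for days observed, although observation ends at healing or discharge. If counts and harms are compared without a time denominator and stays differ, the arm observed for less time would look better.

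On the assumed stopping parameters of 7 v 10 days, the artefact is about 12% to 24% fewer episodes, depending on which schedule governs. For events at an assumed 0.5% a day, the crude risk shifts by about one percentage point with the 21-day cap. The test is badly distorted for raw totals and only modestly for rare events. These figures rest on constant hazards and equal daily rates, and the rejection rates also on independent patients. None of these is given in the document.

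A reader might go further and take 7 and 10 days as the actual mean stays, giving 21 v 30 episodes and a 30% false reduction, or conclude that the harms results are bound to be biased. The document supports neither. It gives no expected stay, and a 10-day mean is impossible if observation ends at day 7.

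This should be corrected before analysis, but it does not invalidate the design.

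**What to change.** Name a model for each outcome, with ward allowed for in every one:

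- **IADS-D and pain scores:** linear mixed model.
- **GLOBIAD category:** mixed proportional-odds model.
- **Incontinence episodes and adverse events:** Poisson or negative binomial model with log(days observed) as offset. Analysing episodes per day is an acceptable alternative.
- **Healing and PI:** time-to-event analysis with the handling of discharge stated. A logistic model without a time term would repeat the fault.
- **PI reporting:** both cumulative risk and rate per 100 patient-days, so that a benefit through faster healing can be told apart from a lower daily rate.

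State whether incontinence is recorded as a total, per day or per assessment. Say what the regression is and to which outcomes it applies. Reconcile the 21-day follow-up (three reviews a week for three weeks, 3 × 3 = 9) with the four assessments and the day 1/3/5/7 schedule, so that the observation window is clear.

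The cost is SAP wording and modest programming in SPSS or R, both already named. The downside is that rare-event models may be unstable with few wards. In that case, compare ward-level rates per patient-day.

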Title: Evaluate the Efficacy of Two Advanced Skin Treatment Regimens in Treating Incontinence-associated Dermatitis: Cluster Randomization Study

Study protocol

Study design

An open-label, cluster randomized, three-group, prospective study will be adopted. Cluster randomization will be used to allocate the selected wards to the experimental or control group for ease of operation (Hemming, Eldridge, Forbes, Weijer, amp; Taljaard, 2017), avoiding confusion on the treatment regimens and cross-contamination of subjects (Sedgwick, 2012). The randomized code for the nursing units will be generated using www.randomizer.org as Treatment 1 or Treatment 2 or Control. Blinding is not possible as the treatment products cannot be “masked”. A purposive sampling on inpatients with IAD will be recruited into the study upon consent. The inclusion and exclusion criteria are as listed in K1 amp; K2. The participants will automatically follow the randomization code selected (implied either control or treatment arm) by the nursing unit he is being admitted.

Study materials

Control

The control regimen for IAD is the current standard of care implemented by the organizations participating in the study. The control regime are combination of treatment - varied practices currently for the treatment of IAD – including the use of potassium permanganate, barrier cream or zinc oxide with skin wipes or soap and water for cleaning

Treatment products

The recommended treatment for IAD should include a structured skin care regimen containing a skin cleanser and a skin protectant. The chemical components recommended as protectants should contain either zinc-based, petrolatum-based, dimethicone-based, or an acrylic polymer. The four preselected products for review are: (1) Conveen easi cleanse and Coloplast Conveen critic barrier (2) 3M No rinse cleanser and 3M Caviton No string Barrier Film (3) 3M No rinse cleaner and 3M Caviton Advanced Skin Protectant(4) Smith and Nephew Moisturizing cleanser and Secura EP cream 30%

Study process

Screening/Recruitment

1. When a potential candidate is identified, the research team members will be activated.
2. Eligible participants from the cluster randomized nursing units will be screened. If they meet the inclusion/exclusion criteria, the PI / co-I will be approached the participants face-to-face.

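### The plan does not say how repeated scores from one patient enter the ANOVA, and several readings it leaves open inflate the error rate or select on healing

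*Combined protocol and SAP*

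**What the plan says.** The trial is three-armed and cluster randomized by nursing unit ("An open-label, cluster randomized, three-group, prospective study will be adopted"). Patients are scored repeatedly. After baseline, the Data collection section states: "Subsequently, 4 more assessments will be made on the participants on the progress of the IAD following treatment(s)/control regimens". Step 12 of the Study day process gives a longer schedule with early exit, at healing or on discharge: "Patients will be followed up three times a week for a maximum of 21 days, or until the IAD has healed". Step 15 makes the early skin assessments conditional: "On Day 3, 5 and 7, an assessment will be made to the skin appearance if the IAD has not resolved". Step 14 has every assessment use IADS-D and GLOBIAD, so the same scales are repeated on the same person. The Data Analysis plan also has photographs reviewed for days 1, 3, 5 and 7.

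Against this, the group comparison is a single sentence: "ANOVA will be used to analyse for group differences". The only other model is a regression adjusted for risk factors, and "A significance level of 0.05 will be used". The plan names no form of ANOVA, outcome, visit, patient term, time term or multiplicity rule. The one correlation it mentions is the intra-cluster coefficient, with a threshold of 0.10, which is framed in terms of clusters and not of visits within a patient.

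**The concern.** Scores taken on one patient over several days are correlated. A plain ANOVA is valid only if each record is independent, so it matters how the visits are put into it. The plan leaves at least four routes open:

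- **Pool all visits.** One patient counts several times, standard errors are too small, and p-values are too low.
- **Test each visit.** The test is repeated, and the 0.05 level no longer holds if any significant visit is taken as success.
- **Repeated-measures ANOVA on complete cases.** Patients with a missing visit drop out. As follow-up stops at healing or discharge, those with full records are mainly those still unhealed and in hospital.
- **One value per patient, tested once.** This avoids the within-patient problem. If the value is a late score among patients still observed, however, it has the same selection as the third route.

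Healing is an outcome that treatment may change, so a comparison restricted by healing no longer compares the randomized groups. An analyst could also choose among the routes after seeing the data.

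**Working it through.** The documents give no sample size, power, effect size or standard deviation, so there is no figure of the plan's own to reproduce. The check asks what happens to the nominal 0.05 under the routes left open.

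**Inputs from the documents:** 3 arms (2 numerator degrees of freedom); significance level 0.05; 4 post-baseline assessments; at most about 3 per week × 3 weeks = 9 reviews.

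**Assumptions (not in the documents):** exchangeable within-patient correlation r of 0.3, 0.5 or 0.7; 30 patients per arm in the simulations; no ward effect; complete visits unless stated.

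**Pooled visits.** With m records per patient the design effect is DE = 1 + (m − 1)r. In large samples the pooled two-degree-of-freedom statistic is DE times a chi-square on 2 df, so the true type I error is P(χ²₂ > 5.991/DE) = 0.05^(1/DE). The number of patients per arm does not enter this formula. For m = 4:

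| r | DE | 0.05^(1/DE) | Simulated (6,000 trials) |
|---|---|---|---|
| 0.3 | 1 + 3×0.3 = 1.9 | 0.207 | 0.205 |
| 0.5 | 1 + 3×0.5 = 2.5 | 0.302 | 0.300 |
| 0.7 | 1 + 3×0.7 = 3.1 | 0.380 | 0.390 |

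**Pooled visits with early exit.** If 30% of patients are assumed to leave after each visit, with at most four visits, the simulated error is about 17%, 24% and 31% at r = 0.3, 0.5 and 0.7 (accurate to about one percentage point). This is smaller than with complete visits but still more than three times 0.05.

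**Separate test at each of four visits, any p < 0.05 counted.** If the tests were independent: 1 − 0.95⁴ = 0.1855. Visits on the same patient are correlated, so the inflation is less: simulated 0.171, 0.159 and 0.131 at r = 0.3, 0.5 and 0.7.

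**One value per patient (mean over four visits), tested once.** Simulated 0.046, 0.050 and 0.052, which is the nominal level. The inflation therefore comes from how visits are handled and not from ANOVA itself.

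**Selection.** This needs no arithmetic. Step 12 ends follow-up at healing or discharge, and step 15 assesses Days 3, 5 and 7 only in unresolved cases. Unless a score is assigned to healed patients, the observed scores at a later visit come only from patients who have neither healed nor gone home.

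**The case against.** The strongest reply is that the plan never says visits will be pooled or that each visit will be tested. ANOVA could mean a repeated-measures form, which does have a patient term. It could also mean one value per patient, such as a change score. The listed outcomes include healing rates, and the plan mentions a risk difference or mean difference; both fit a single value per patient. On that reading neither form of inflation follows. This stands: a reader might infer that the trial will run a faulty pooled or per-visit test, and the documents do not support that. They support only that nothing rules it out.

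A reader might also infer that every patient contributes at least four follow-up records, or take nine pooled visits as the typical case. Neither is supported. Patients who heal or are discharged early have fewer records, and a nine-visit calculation would need nobody to heal or leave in 21 days. The same applies to exclusion of healed patients from later comparisons: the documents do not state it, but they give no score for those patients either.

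Finally, patients are nested in wards, so a ward-level summary analysis, or a ward-clustered variance with enough wards, would absorb much of the within-patient correlation. That is fair, and the pooling inflation should not be added to any allowance for ward clustering. But the plan does not commit to such an analysis, and it would not settle which visit is primary or how records that end early are handled.

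**Conclusion.** The concern holds as a gap in specification with material consequences. The plan schedules repeated scores per patient and does not say how they enter the group comparison. Under pooling the type I error is about 21% to 38% for four complete visits, and lower but still inflated with early exit. Under four separate tests with any significant result counted it is about 13% to 17%. Complete-case or observed-only late-visit analyses instead give a sample selected on healing and discharge. These error rates rest on assumed correlations of 0.3 to 0.7, no ward effect and, for the simulations, 30 patients per arm. They describe what the wording allows, not what the trial is known to intend. A single pre-specified value per patient would keep the level near 0.05 as far as within-patient correlation goes, but the plan does not name one.

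**What to change.** Replace ANOVA for the IADS-D score with one pre-specified longitudinal mixed model:

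- **Terms:** arm, visit, arm-by-visit and the Day 0 score, with a patient random effect, a ward random effect and small-sample degrees of freedom (Satterthwaite or Kenward-Roger).
- **Primary test:** the arm contrast at one named visit, as the single primary test. Pain is secondary. The two visit schedules (four further assessments, or three a week for up to 21 days) should be reconciled so that the visit can be named.
- **Healed patients:** scored at the healed value at later visits.
- **Patients discharged unhealed:** treated as missing under the model.
- **Sensitivity analysis:** one covering both of these rules.

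The number of wards is not stated, so the plan needs a fallback. If there are too few wards per arm to estimate a ward effect, analyse one pre-specified summary per patient, aggregated to ward level. If there is only one ward per arm, state that arm and ward effects cannot be separated; no model cures that.

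The cost is SAP wording and somewhat more modelling, with scores already planned and in R, which is already named. The main drawback is the assumption that healed skin does not relapse. A constant healed score also fits a normal model imperfectly, which is a further reason for the sensitivity analysis.

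### Pain is listed both as a baseline parameter and as an outcome, but no planned model names the baseline pain score, so the pain comparison gives up some precision that could be had at little cost

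*Combined protocol and SAP*

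**What the plan says.** - **Data collection** introduces its list with "Baseline parameters and other outcome measures that will be collected include the pain scores" and continues: "Subsequently, 4 more assessments will be made on the participants on the progress of the IAD".
- **Data Analysis plan**, last paragraph, puts pain first among the outcomes: "The outcome measures include the pain scores, assessment scores for IAD and healing rates".
- **Data Analysis plan**, first paragraph, gives two inferential methods. One is "ANOVA will be used to analyse for group differences". The other is "Multivariate regression will be used to evaluate the effect of treatment regimens, adjusting for risk factors". The risk factors are not listed anywhere.
- The effect is to be reported as follows: "The measure of effect (risk difference or mean difference) and a confidence interval or measure of variation will be examined".
- On clustering, the plan refers to an "ICC of 0.10 used as the acceptable determine for cluster independence during observations". This is a threshold for judging independence, not a design input.

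The plan describes no analysis of covariance, change score or repeated-measures model. It names no baseline value of any outcome as a covariate, and it states no time point for the pain comparison.

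**The concern.** If each patient's pain is known before treatment and again afterwards, the baseline score is usually among the better predictors of the later one. Comparing follow-up pain without it has two effects. Variation between patients that the baseline could explain stays in the error term, which widens the confidence interval. Any difference between the arms in starting pain also passes, in proportion to the correlation, into the estimated regimen effect.

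The second effect deserves some attention here because wards are allocated, not patients, and each patient takes the regimen of the admitting ward. Chance differences between arms at baseline can therefore be larger than with individual randomization of the same number of patients.

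At stake are the width of the interval for pain and its protection against chance imbalance. If the covariates are not named in advance, the choice would also be made after the data have been seen.

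**Working it through.** **Inputs from the documents.** Three groups, randomized by ward. Significance level: "A significance level of 0.05 will be used" (taken here as two-sided, which the plan does not state). The ICC of 0.10 is borrowed from the plan's threshold. The plan has no sample size, power, effect size, standard deviation or correlation, so it has no figure of its own to reproduce.

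**Assumptions.** Correlation rho between Day 0 and follow-up pain of 0.3, 0.5 or 0.7; a pairwise comparison with 80% power when unadjusted; m = 10 patients per ward, with 5 and 20 as a range.

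**Step 1: ignoring wards.** Adjustment multiplies the residual variance by V = 1 − rho². Adjusted power is Φ((1.96 + 0.842)/√V − 1.96).

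| rho | V | Power |
|---|---|---|
| 0.3 | 0.91 | 84% |
| 0.5 | 0.75 | 90% |
| 0.7 | 0.51 | 98% |

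**Step 2: allowing for wards.** Suppose that baseline pain explains only variation between patients within a ward. The variance of a ward mean, in units of the total variance, is ICC + (1 − ICC)/m unadjusted and ICC + (1 − ICC)(1 − rho²)/m adjusted. With ICC 0.10 and m = 10, the unadjusted value is 0.10 + 0.90/10 = 0.190. The adjusted value at rho 0.5 is 0.10 + 0.90 × 0.75/10 = 0.1675, so V = 0.1675/0.190 = 0.882. The same power formula gives:

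| rho | V | Power |
|---|---|---|
| 0.3 | 0.957 | 82% |
| 0.5 | 0.882 | 85% |
| 0.7 | 0.768 | 89% |

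At rho 0.5 the gain is 4.7 points (0.847 − 0.800). Over m = 5 to 20, V runs from 0.942 to 0.972 at rho 0.3, from 0.839 to 0.922 at rho 0.5, and from 0.685 to 0.848 at rho 0.7. If baseline pain explained between-ward variation to the same degree, V would return to the step 1 values.

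**Step 3: starting differences.** An arm difference of d standard deviations in Day 0 pain shifts the expected unadjusted follow-up difference by rho × d. With d = 0.5 and rho = 0.5 the shift is 0.25 SD. To see how often such a gap arises by chance, assume 40 patients per arm. Without clustering, the standard error of the baseline difference is √(2/40) = 0.224 SD, and a gap of 0.5 SD or more in either direction has a probability of about 2.5%. With four wards of 10 per arm and a baseline ICC of 0.10, the standard error is √(2 × 0.190/4) = 0.31 SD and the probability is about 10%.

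**The case against.** **Baseline pain may be among the risk factors.** The term is undefined, and every participant already has IAD, so it need not mean predictors of onset. A reader might infer that the plan excludes baseline pain. The text does not support that: baseline pain is unspecified. The gap remains, because no model names it and ANOVA as stated carries no covariate.

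**The pain schedule is inferred.** The Data collection sentence mixes baseline items with outcomes such as healing rates and adverse events, which cannot be Day 0 values. The Day 0 steps under Study day process do not mention pain. The four later assessments concern the progress of the IAD, and item 14 says that all assessments use two IAD tools. Scoring pain before and after is the natural reading of an outcome that is also introduced under baseline parameters, but the protocol should confirm it.

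**The gain may be small.** This stands. The figures that ignore wards are the less relevant ones in this design, and with wards allowed for the gain can be under 5 points even at rho 0.5. Nor do the documents show how widely pain varies between patients before treatment.

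**A stronger reading is that the unadjusted test has an inflated error rate.** With 40 per arm and rho 0.5, and ignoring clustering, a false-positive rate of about 17% can be calculated. It holds only given a 0.5 SD starting gap, which chance alone produces about 2.5% of the time in that same setting. It is not the error rate of the test, and the documents report no such imbalance.

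**Clustering is the larger issue.** It is a separate one, but it limits the remedy: a patient-level analysis of covariance without a ward term would give falsely narrow intervals.

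**Conclusion.** The point holds as a modest, inexpensive improvement. No planned model names the baseline pain score, although pain is introduced under baseline parameters and is an outcome. The direction is clear: with any material correlation between baseline and follow-up pain, adjustment narrows the interval and removes the part of the effect estimate that is due to unequal starting pain.

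The size is not known. In the case closest to this design, 80% power becomes about 82% to 89% over rho 0.3 to 0.7. That rests on an assumed correlation, ward size and starting power, an ICC taken from the plan's threshold, and adjustment that acts only within wards. The corresponding 84% to 98% applies only if clustering is ignored.

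This concerns precision on one of several outcomes, none of which is named as primary. It does not make the pain comparison invalid.

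**What to change.** For pain, replace the ANOVA with a specified model:

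- **Outcome:** follow-up pain score at one stated time point. The plan should also say how patients are handled whose follow-up ends earlier through healing or discharge.
- **Covariates:** regimen and the patient's Day 0 pain score, named before the data are analysed.
- **Clustering:** ward accounted for, for example by a ward random effect or a ward-level analysis.
- **Reporting:** adjusted mean difference with its confidence interval as the pain result; any unadjusted difference as description only.
- **Data:** confirm in the protocol and the case record form that pain is scored at Day 0 and at follow-up, and give a simple rule for a missing Day 0 score.

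If pain is already scored at both times, this needs no new patients or visits. The cost is a short rewrite of the analysis text, one degree of freedom for the covariate, and the extra work of fitting a model that respects wards, which the design calls for in any case. If Day 0 pain is not yet scheduled, one score per patient is added to an existing assessment.
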